	
≤ 14 days prior to initiation of study drug, Cycle 1 (Day 1 and weekly), and prior to treatment on Day 1 of subsequent cycles, 30-Day Follow-Up.
 
Performance Status: ≤ 14 days prior to initiation of study drug, Cycle 1 (Day 1 and weekly), and prior to treatment on Day 1 of subsequent cycles, 30-Day Follow-Up.
 
12-Lead ECG: ≤ 14 days prior to initiation of study drug and prior to treatment on Day 1 of Cycle 2 and Cycle 3, if clinically indicated.

Statistical Analysis
	
Efficacy Assessments:
 
 • 18-week PFS is defined as the proportion of patients whose disease has not progressed at 18 weeks after getting etirinotecan pegol. • Tumor response is defined as a complete response (CR) or partial response (PR) by RECIST 1.1 criteria, which will be evaluated by CT-scan every other cycle. • OS is defined as the time from enrollment to death from any cause. 
Safety Assessments:
 
 • The maximum grade for each type of adverse events (AEs) will be recorded for each patient based on NCI CTCAE version 4.0, and frequency tables will be reviewed to determine AE and toxicity (unrelated, unlikely, possible, probably, or definitely related to study treatment) patterns in each group. • A single-stage design will be used to assess the primary endpoint separately for each. Based on this, the primary endpoint of this trial will be the proportion of patients who are progression-free at 18 weeks.

Study Schema

INVESTIGATOR STUDY ELIGIBILITY VERIFICATION FORM

Subject Name: (Network sites use subject initials): _____

Medical Record No.: (Network sites use subject ID): _____

Title: A Phase II Study of Single Agent Topoisomerase-I Inhibitor Polymer Conjugate, Etirinotecan Pegol (NKTR-102), in Patients with Relapsed Small Cell Lung Cancer

INCLUSION CRITERIA				
Yes	No	N/A	All answers must be "YES or "N/A" for patient enrollment.	Date
			1. Written informed consent granted prior to initiation of any study-specific screening procedures, given with the understanding that the patient has the right to withdraw from the study at any time, without prejudice.	
			2. 18 years of age or older.	

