9 SAFETY EVALUATION

9.1 Adverse Events

9.1.1 Definition

An adverse event or adverse experience (AE) is any untoward medical occurrence associated with the use of a drug in humans, whether or not considered drug related. Therefore, an AE can be ANY unfavorable and unintended sign (including an abnormal laboratory finding), symptom, or disease temporally associated with the use of a medicinal (investigational) product, whether or not considered related to the medicinal (investigational) product (attribution of ‘unrelated’, ‘unlikely’, ‘possible’, ‘probable’, or ‘definite’).

An AE is considered “unexpected” if it is not listed in the investigator brochure or is not listed at the specificity or severity that has been observed; or if an investigator brochure is not required or available, is not consistent with the risk information described in the general investigational plan in other study-related documents.

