9.1.3 Reporting Adverse Events

Table 7. Guidelines for Routine Adverse Event Reporting for Phase II Studies (Regardless of Expectedness)

Attribution	Grade 1	Grade 2	Grade 3	Grade 4
Unrelated			X	X
Unlikely			X	X
Possible	X	X	X	X
Probable	X	X	X	X
Definite	X	X	X	X

- Routine AEs occurring between the start date of intervention until 30 days after the last intervention or until the event has resolved, the study patient is lost to follow-up, the start of a new treatment, or until the study investigator assesses the event(s) as stable or irreversible, will be reported. New information will be reported after it is received.

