Progression-free survival is defined as the time from registration to the date of first documented disease progression or death. Survival time is defined as the time from registration to death due to any cause. Patients who loss-to-follow-up or alive at time of analysis will be censored at the last contact of known alive. The distribution of time to disease progression and survival time will be estimated in each group using the method of Kaplan–Meier. Probability of PFS at 18 weeks and 24 week and probability of survival at 3, 6, and 9 months will be estimated. All eligible and treated patients will be included in the analysis of the primary endpoint.

All adverse events, regardless of attribution, will be summarized (overall and by group).³⁴

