11.5 Safety Analysis

As per NCI CTCAE v 4.0, the term toxicity is defined as adverse events that are classified as either possibly, probably, or definitely related to study treatment. Non-hematologic toxicities will be evaluated via the ordinal CTC standard toxicity grading. Hematologic toxicity measures of thrombocytopenia, neutropenia, and leukopenia will be assessed using continuous variables as the outcome measures (primarily nadir) as well as categorization via CTC standard toxicity grading. Overall toxicity incidence as well as toxicity profiles by dose level, patient and tumor site will be explored and summarized. Frequency distributions, graphical techniques and other descriptive measures will form the basis of these analyses.

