11.6 Adverse Event

The number and severity of all adverse events (overall, by regimen, and by dose level if appropriate) will be tabulated and summarized. The Grade 3+ adverse events will also be described and summarized in a similar fashion. This will provide an indication of the level of tolerance for this treatment combination in this patient group.

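### The all-attribution adverse event summaries in 11.1, 11.6 and the synopsis do not match Table 7, which does not call for routine reporting of Grade 1-2 events judged unrelated or unlikely

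*Combined protocol and SAP*

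**What the plan says.** **Analysis side.** Section 11.1 plans: "All adverse events, regardless of attribution, will be summarized (overall and by group". Section 11.6 plans: "The number and severity of all adverse events (overall, by regimen, and by dose level if appropriate) will be tabulated and summarized"; it then describes Grade 3+ events as an additional summary, so the main table is meant to include Grades 1 and 2. The synopsis (Safety Assessments) says: "The maximum grade for each type of adverse events (AEs) will be recorded for each patient based on NCI CTCAE version 4.0". It adds that frequency tables will be reviewed across all five attribution categories, ending "unrelated, unlikely, possible, probably, or definitely related to study treatment) patterns in each group".

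**Definition.** Section 9.1.1 counts an event as an adverse event "whether or not considered related to the medicinal (investigational) product (attribution of ‘unrelated’, ‘unlikely’, ‘possible’, ‘probable’, or ‘definite".

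**Reporting side.** Section 9.1.3 contains Table 7, titled "Guidelines for Routine Adverse Event Reporting for Phase II Studies (Regardless of Expectedness". The rows for possible, probable and definite are marked at Grades 1 to 4. The rows for unrelated and unlikely are marked at Grades 3 and 4 only. The text under the table sets the time window for reporting routine events.

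**Related-only analysis.** Section 11.5 is narrower by design: "the term toxicity is defined as adverse events that are classified as either possibly, probably, or definitely related to study treatment".

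**The concern.** The analysis text asks for a table that the reporting rule may not fill. If Table 7 decides what reaches the database, one table applies two inclusion rules: any cause at Grades 3-4, and essentially drug-related events at Grades 1-2. Its label would not tell the reader this.

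Three things would be at stake in that case:

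- Any-grade incidence of an event type would be too low, and the share of events that are severe would look too high.
- The maximum grade per patient could be understated. A patient with related Grade 1 fatigue and, at another visit, Grade 2 fatigue judged unrelated would be shown at Grade 1.
- Low-grade counts would depend on investigator attribution. Section 9.1.2 frames attribution as a judgement between the drug and the patient's clinical state. In an unblinded single-arm trial, symptoms such as fatigue, nausea or anorexia can plausibly be assigned to either. If attribution habits differed between Groups A and B, the by-group summary would reflect that difference as well.

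**Working it through.** There is no stated figure to reproduce; the check sets the passages side by side.

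**1. Count the Table 7 cells.** Five attributions by four grades gives 5 × 4 = 20 cells. Marked: 3 rows × 4 grades + 2 rows × 2 grades = 12 + 4 = 16. Blank: 20 − 16 = 4, namely unrelated Grade 1, unrelated Grade 2, unlikely Grade 1 and unlikely Grade 2. The same two cells are empty in both rows and the other three rows are full, so the pattern reads as a deliberate rule.

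**2. Compare with each planned output.**

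| Output | Events needed | Filled by Table 7 alone? |
|---|---|---|
| 11.1, all AEs, overall and by group | All 20 cells | No, 4 cells missing |
| 11.6, number and severity of all AEs | All 20 cells | No, 4 cells missing |
| Synopsis, maximum grade per type, five attributions | All 20 cells | No, 4 cells missing |
| 11.6, Grade 3+ summary | Grades 3-4, any attribution | Yes |
| 11.5, toxicity | Possible, probable, definite, all grades | Yes |

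Table 7 has no Grade 5 column, but death is a serious event under 9.2.1 and is reported by that route.

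**3. Allow for serious events.** Section 9.2.2 requires all new SAEs to be reported from consent to 30 days after the last intervention (or the start of a new treatment, if sooner), with no attribution filter. Section 14.1 puts a serious event on the Adverse Event page as well as the SAE form. A serious Grade 1-2 event judged unrelated or unlikely would therefore still be captured. The possible gap is confined to non-serious events in the four blank cells.

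**4. Express the shortfall.** For one event type, let *q* be the true any-grade proportion of patients. Let *f* be the share of those patients whose every occurrence was Grade 1-2, non-serious and judged unrelated or unlikely. With entry limited to Table 7 plus SAEs:

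- tabulated proportion = *q* × (1 − *f*)
- shortfall = *q* × *f*

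One occurrence judged possible, or one at Grade 3 or higher, keeps the patient in the table, so *f* is a patient-level share and not the share of events. The documents give no value for *f*. Logically it lies anywhere from 0 (no shortfall) to 1 (the event type disappears), so the direction is known and the size is not.

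**5. Compare 11.1 with 11.5.** Under Table 7 alone, the all-attribution table and the related-only toxicity table would hold the same Grade 1-2 events apart from serious ones. The plan defines the two outputs differently, so that overlap cannot be what was intended.

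**The case against.** The strongest reply is that Table 7 is about reporting, whereas entry on the case report form is governed elsewhere. Sections 9.1.1.1 to 9.1.1.4 say what is recorded on the CRF and contain no filter by attribution or grade. Where a restriction is intended it is explicit, as in 9.1.1.3, which limits laboratory abnormalities to clinically significant ones needing active management. The synopsis says the maximum grade of each event type is recorded for each patient, and sections 7.8 to 7.12 schedule an adverse event evaluation at every treatment and 30-day visit. On that reading every event is entered and the table is complete.

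This stands in part. A reader might infer that low-grade unrelated events are not collected, that the planned table will be wrong, or that its Grade 1-2 counts contain only events attributed to the drug. The documents do not support any of these. The first two depend on sites treating Table 7 as the entry rule, and the third overlooks serious events. A percentage understatement for fatigue or any other event is likewise unsupported, because no share judged unrelated or unlikely is given.

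The reply does not remove the inconsistency. The CRF sections deal with diagnoses, secondary events, laboratory values and pre-existing conditions. None says that events outside Table 7 are still to be entered. A site following Table 7 literally would be compliant and would leave the four cells empty; a site following the synopsis would not.

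It is also fair to say that little depends on the affected output. The secondary objective in 3.2 concerns toxicity, which 11.5 defines as related events, and the decision rules in 11.1 use only 18-week progression-free counts.

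**Conclusion.** The inconsistency is real as written and minor. Three analysis statements cover all adverse events at every attribution, while the only attribution-by-grade rule omits Grade 1-2 events judged unrelated or unlikely.

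The consequence is conditional. If sites enter only what Table 7 requires, the all-attribution summaries will be incomplete for non-serious Grade 1-2 events and will understate any-grade incidence. The size cannot be estimated from the documents. If sites enter every event, the tables are complete.

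The Grade 3+ summary, the related-event toxicity analysis in 11.5, the primary endpoint and its decision rules are unaffected on either reading. The conclusion assumes that the four blank cells are intended and that serious events reach the Adverse Event page as 14.1 states.

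**What to change.** Reconcile Table 7 with sections 11.1 and 11.6 and the synopsis, in one of two ways.

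1. **Align collection with the tables.** Mark the four blank Table 7 cells, or add a sentence in 9.1.3 that events of every grade and attribution are entered in the eCRF whatever Table 7 requires for reporting. The cost is some extra low-grade data entry; no visits are added, because adverse events are already evaluated at each one.
2. **Align the tables with collection.** Restate 11.1, 11.6 and the synopsis as covering Grade 3 or higher events of any attribution, Grade 1-2 events judged at least possibly related, and all SAEs. Footnote each table with that rule. The cost is wording only, but the tables can then not be read as all-cause incidence at low grades.

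Either option removes the ambiguity. The first keeps the all-cause summary that the analysis sections describe.

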11.2 Randomization

This is a nonrandomized study. No randomization scheme will be generated. Subjects will be assigned to each group based on their relapsed time.

11.3 Demographics and Baseline Characteristics

Descriptive statistics (as appropriate: n, percent, mean, median, min and max) will be used to summarize demographic and baseline characteristics.

11.4 Efficacy Analysis

Objective tumor response will be tabulated overall (and by dose level if appropriate). Best Response is defined to be the best objective status recorded from the start of the treatment until disease progression/recurrence (taking as reference for progressive disease the smallest measurements recorded since the treatment started). The patient's best response assignment will depend on the achievement of both measurement and confirmation criteria. The RECIST 1.1 criteria will be used for solid tumor evaluation and patients will be re-evaluated every other cycle. Responses will be summarized by simple descriptive summary statistics delineating complete and partial responses as well as stable and progressive disease in the cohorts (overall and by tumor group).

11.5 Safety Analysis

As per NCI CTCAE v 4.0, the term toxicity is defined as adverse events that are classified as either possibly, probably, or definitely related to study treatment. Non-hematologic toxicities will be evaluated via the ordinal CTC standard toxicity grading. Hematologic toxicity measures of thrombocytopenia, neutropenia, and leukopenia will be assessed using continuous variables as the outcome measures (primarily nadir) as well as categorization via CTC standard toxicity grading. Overall toxicity incidence as well as toxicity profiles by dose level, patient and tumor site will be explored and summarized. Frequency distributions, graphical techniques and other descriptive measures will form the basis of these analyses.

11.6 Adverse Event

The number and severity of all adverse events (overall, by regimen, and by dose level if appropriate) will be tabulated and summarized. The Grade 3+ adverse events will also be described and summarized in a similar fashion. This will provide an indication of the level of tolerance for this treatment combination in this patient group.

12 CORRELATIVE DATA ANALYSIS

Correlation between correlative study (pharmacogenetic analysis) and other outcome measures like toxicity and response will be carried out in an exploratory manner as described below.

12.1 Pharmacogenetic Analysis

The genes that have been associated with irinotecan pharmacodynamic and pharmacokinetic pathways include those responsible for activation, inactivation and transport of the drug. These genes include *ABCB1*, *ABCC2*, *ABCG2*, *BCHE*, *CES1*, *CES2*, *CYP3A4*, *CYP3A5*, *SLCO1B1*, *TOPI*, *UGT1A1*, *1A3,1A4,1A6*, *1A7,1A8*, *1A9* and *UGT1A10*. As NKTR-102 is a conjugate of irinotecan, most of the irinotecan pathway genes may interact with it thus resulting in similar phenotypic effects. Hence, several genetic variants associated with the pathways may contribute to the clinical outcome of NKTR-102 therapy. Some of the well-known genetic variants that have been associated with irinotecan clinical outcomes include the polymorphic repeat in *UGT1A1* promoter region (*UGT1A1**28, rs8175347; *UGT1A1**93) and the *ABCB1* (1236C > T, 2677G > T/A, 3435C > T), *ABCC2* (-24C > T, 1249G > A, 3972C > T), and *ABCG2* (34G > A, 421C > A) polymorphisms. It is reported that nearly 50% of the variations in neutropenia among individuals could be explained by a combination of genetic polymorphisms and non-genetic covariates, with gene combinations attributing to 28% of the variations, suggesting a polygenic basis for neutropenia.³² *UGT1A1**28 and *93 genotypes have been associated with toxicity; *ABCC2* 3972C > T with severe diarrhea in both Korean and European patients while *SLCO1B1**5 allele is reported to be associated with increased risk of severe neutropenia in Asians, and the *SLCO1B1**1b allele is suggested to be protective of neutropenia.³²⁻³⁵

This Phase I study will initially focus, in an exploratory manner, on the primary genes which will activate (*CES1*, *CES2*, *CYP3A4*, *CYP3A5*) and inactivate (*UGT1A1*) NKTR-102. It is hypothesize that germline polymorphic variants in *CES1*, *CES2*, *CYP3A4*, *CYP3A5* and *UGT1A1* may affect toxicity as well as response to NKTR-102 therapy.

SNP Identification: We will generate tagSNPs from National Center for Biotechnology Information (NCBI), HapMap and/or the Genome Variation Server databases using the Caucasian SNP information for these 5 genes in addition to using SNPs previously reported in literature. These SNPs will be selected with sufficient frequency that its impact on the clinical outcome at a population level would be meaningful and have some degree of likelihood to alter the function of the gene in a biologically relevant manner. Fifty-three SNPs have been identified for genotyping.

Genotyping: The tagSNPs will be genotyped using the MassARRAY Compact system (Sequenom) at RPCI as previously described.³⁶ Whenever possible, published methods and primers will be used for polymorphic variants such as *UGT1A1**28.

13 ETHICAL AND REGULATORY STANDARDS

13.1 Ethical Principles

This study will not be initiated until the protocol and informed consent document(s) have been reviewed and approved by a properly constituted Institutional Review Board (IRB) or Independent Ethics Committee (IEC). Each subject (or legal guardian) shall read, understand, and sign an instrument of informed consent prior to performance of any study-specific procedure. It is the responsibility of the investigator to ensure that the subject is made aware of the investigational nature of the treatment and that informed consent is given.

The Investigator is responsible for the retention of the subject log and subject records; although personal information may be reviewed by authorized persons, that information will be treated as strictly confidential and will not be made publicly available. The investigator is also responsible for obtaining subject authorization to access medical records and other applicable study specific information according to Health Insurance Portability and Accountability Act regulations (where applicable).

This study will be conducted in compliance with all applicable laws and regulations of the state and/or country and institution where the subject is treated, in accordance with the Declaration of Helsinki, Good Clinical Practice, and according to the guidelines in this protocol, including attached appendices.

13.2 Informed Consent

The Investigator is responsible for obtaining written consent from each subject or the subject's legally authorized representative in accordance with ICH-GCP guidelines using the approved informed consent form, before any study specific procedures (including screening procedures) are performed. The informed consent form acknowledges all information that must be given to the subject according to ICH-GCP, including the purpose and nature of the study, the expected efficacy and possible side effects of the treatment(s), and specifying that refusal to participate will not influence further options for therapy. Any additional information that is applicable to the study must also be included. Additional national or institutionally mandated requirements for informed consent must also be adhered to. The subject should also be made aware that by

signing the consent form, processing of sensitive clinical trial data and transfer to other countries for further processing is allowed.

The Investigator shall provide a copy of the information sheet and of the signed consent form to the subject and the signed original shall be maintained in the Investigator File. A copy of the signed consent form must be filed in the subject file. At any stage, the subject may withdraw from the study and such a decision will not affect any further treatment options.

14 STUDY RESPONSIBILITIES

14.1 Data Collection

Data entry into the database is to be completed in a timely fashion (approximately within 28 days) after the subject's clinic visit. If an AE is considered serious it is captured on both the Adverse Event page and the Serious Adverse Event Form, which is handled in an expedited fashion.

Data management activities will be performed using EXPeRT. EXPeRT is a suite of software tools that enables the collection, cleaning and viewing of clinical trial data. CRS data management will design the study-specific database and facilitate its development by the EXPeRT Information Technology team. Once the database design is approved by the Investigator, Statistician, and Clinical Research Coordinator, the database will be put into production and data entry can begin. Data can be entered and changed only by those with the rights to do so into the eCRFs. EXPeRT is compliant with all relevant technical aspects of relevant GCP guidelines.

- The system can generate accurate copies of stored data and audit trail information in human readable form.
- System access is limited to authorized individuals through the controlled assignment of unique ID and password combinations.
- The system is designed to periodically force users to change their passwords and verifies that user ID and password combinations remain unique.
- The system automatically generates a permanent time-stamped audit trail of all user interactions.

When data entry is complete, data management will review the data and will query any missing, incomplete, or invalid data points for resolution by the Clinical Research Coordinator and Investigator. Once all queries have been resolved, the data can be released to the statistician for analysis.

